### **Methods to monitor and address missing data (MD- 1-3, 5)**

We have identified the following 5 variables as exhibiting data missingness (MD-1) in our dataset for this study:

- Variable 1: Geocoded poverty level
- Variable 2: Geocoded education level
- Variable 3: Member-level income level
- Variable 4: Member-level net worth
- Variable 5: Member-level deductible Level

**Missing poverty, education, income, and net worth data:** We will use 3 methods to accommodate missingness (MD- 2-3): (a) multiple imputation, (b) modeling missingness as a member-level characteristic, and (c) excluding members with missing data. If findings differ, we will present results using all 3 methods in manuscripts or attached appendices. We will use SAS procedures PROC MI and PROC MIANALYZE to impute the missing individual level covariates and conduct the statistical analyses under the assumption of missing at random. The SAS procedure PROC MI will impute the missing variables (including individual net worth, income level, poverty level and education level) using other available variables such as age, gender, census block level income, poverty, education etc. Then we will use PROC MIANALYZE to analyze the imputed data. We will also explore certain Bayesian imputation techniques to handle missing data in case missing is not at random and compare the results. If the degree of missingness for member-level credit report data is found to be too great, we will still be able to use geocoded poverty and education census block-level data, for which missingness has been less than 1% in the study team's prior work using this data source.

**Missing Deductible Level Data:** Through our data vendor, Optum, we will have detailed benefit information for ~80% of employer groups obtaining coverage from the health plan. For smaller employers (with approximately 100 or fewer employees), we will use a benefits type variable that is not missing for smaller employers. For larger employers with missing deductible levels, we will take advantage of the fact that health insurance claims data are the most accurate source for assessing out-of-pocket obligations among patients who utilize health services. Our claims data contain an in-network/out-of-network deductible payment field. For patients who use expensive or frequent services, the sum of their yearly deductible payments will add up to clearly identifiable exact amounts such as \$500.00, \$1000.00, \$2000.00, etc. When several members have these same amounts, it provides strong evidence that the employer offered such an annual deductible level. It will also be possible to detect employers that offer choices of deductible levels when multiple employees have deductibles at two or more levels, such as 20 employees with an annual amount of \$1000.00 and 12 employees with \$500.00. For employers with at least 10 workers, we therefore will sum each employee's in-network deductible payments and number of claims over the enrollment year and plan to assess other key characteristics such as percentage with Health Savings Accounts. On a randomly selected half of the employer data set that contains our calculated employer characteristics (such as the percentage of patients with deductible levels between \$1000-\$2500) as

well as actual deductible amounts, we will use a logistic model that predicts the 5-level outcome of deductible amounts (\$250/\$250-\$499/\$500-\$999/\$1000-\$2499) based on multiple aggregate employer characteristics such as the first and second most common whole number deductible value, the percentage with Health Savings Accounts, the median deductible payment, the percentage of employees using services, the employer size, the percentage of employees with deductible levels between \$100-\$250/\$250-\$500/ \$500-\$1000/ \$1000-\$2500/ >\$2500, etc. This predictive model will output the probability that employers had deductibles in the 5 categories (summing to 1) and we will assign the employer to the level that has the highest probability. If we detect employers that have 10 or more employees with whole number deductible levels both above and below \$500 (e.g. \$250.00 and \$1500.00), we will assign the employers' category as "choice." If 100% of employees have Health Savings Accounts, we will also overwrite any previous assignment to classify the employer as a high-deductible employer. We will test the predictive model on the other half of the sample for which we have actual deductible levels. We have previously used a similar algorithm and, at employers with 75-100 workers, we found sensitivity and a specificity of over 96% (MD-5).

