2. **Use of asthma rescue medications (Aims 2-3):** We will assess use of albuterol and levalbuterol inhalers, the primary asthma rescue medications prescribed to patients, which are subject to the deductible in HSA-HDHPs without PDLs, free in HDHPs with PDLs, and subject to copayments in traditional plans. All albuterol and levalbuterol inhalers are brand-name drugs containing 200 puffs each. We will exclude nebulized versions as these are predominantly used by younger children and do not come in standardized doses. As in our prior study, we will measure the standardized number of inhalers dispensed per month based on National Drug Code (NDC) in pharmacy claims. Given the inter-relationship between rescue and controller medication use, we will also measure the ratio of controller medications to total asthma medications, a metric for which higher values are associated with better asthma control and lower rates of asthma-related ED visits.
3. **Use of spacers and nebulizer machines (Aims 2-4):** Based on input from patients and stakeholders, and with additional input from questions from added questions in the qualitative interview guide in response, we will assess changes in the number of spacers and nebulizer machines received by study patients, based on claims data. We will measure changes in receipt of spacers and nebulizer machines after a switch to an HSA-HDHP vs. remaining in a traditional plan to see if changes in the cost-sharing for these devices leads to a decrease in receipt and an increase in OOP costs to families.
4. **Asthma-related ED visits and hospitalizations (Aims 2-3):** As a measure of potentially avoidable short-term complications, we will measure asthma-related ED visits and hospitalizations that have a primary ICD-10 diagnosis code for asthma.
5. **OOP health care costs (Aim 4):** We will calculate consumer price index (CPI)-adjusted OOP costs for asthma medications and other health services, summing deductible, co-pay, and coinsurance amounts, aggregated into annual measures. Financial burden due to OOP costs will be defined as annual family OOP costs as a percent of family income, with cutpoints of >5% and >10% to indicate financially burdensome OOP costs.

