*Hypothesis (see Figure 2): Enrollees with asthma in HSA-HDHPs without PDLs will have worse adherence to controller medications, greater need for rescue medications, and higher rates of asthma-related ED visits and hospitalizations, with widening of income and racial/ethnic disparities; the addition of a PDL will improve use of controllers and rescue medications, reduce ED and hospitalization rates, and lessen disparities.*

Analyses will compare changes in outcomes from baseline to up to three years of follow-up among 1) asthma patients switched to HSA-HDHPs without PDLs from traditional plans vs. matched patients whose employers remain in traditional plans; and 2) patients switched to HSA-HDHPs with PDLs from traditional plans vs. matched controls remaining in HSA-HDHPs without PDLs. Sensitivity analyses will compare patients switched to HSA-HDHPs with PDLs from traditional plans vs. those who remain in traditional plans to examine the combined impact of both increasing the deductible and gaining a PDL. We will use separate regression models to compare year-to-year changes for each intervention group relative to its matched control group, rather than including all patients in a single model with multiple interaction terms. For secondary analyses of enrollees in the larger set of plan types that include PDLs, we will compare enrollees who are switched from plans with no PDL to plans with a PDL vs. those who remain in plans without a PDL. These analyses will match and adjust for different baseline plan types and deductible levels.

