In all statistical models, we will include key individual-level predictors from Table 2 to adjust for potential confounding. To determine the impact of HSA-HDHP with and without PDLs on vulnerable populations (RQ-4) and test for heterogeneity of treatment effects among vulnerable populations (HT-1-4), we will first perform stratified analyses, comparing outcomes between intervention and control subgroups defined by the binary measures of the risk factors of interest (low income, minority race/ethnicity, moderate-severe asthma, presence of other chronic conditions (including co-morbid diagnosis of COPD; we will also conduct analyses limited to ages 4-50 to remove the effect of COPD co-morbid diagnoses), high ACG morbidity). We hypothesize that these vulnerable subgroups will have worse adherence, more frequent adverse clinical outcomes, and higher OOP costs. We will use three-way interaction terms (insurance type \* study period \* subgroup) to test for statistical differences between subgroups in the impact of the change to an HSA-HDHP with PDL vs. remaining in a traditional plan. Heterogeneity of treatment effect analyses for these key variables will be reported along with overall findings from the combined population. Given that we will be conducting sub-group analyses to test for heterogeneity of treatment effect based on race/ethnicity and income using three-way interaction terms, we elected to separate the analyses of heterogeneity of treatment effect by age group into Aim 3 (described below), rather than add a fourth interaction term to the analyses in Aim 2. In Aim 2 analyses, we will include

both adults and children together, with age included as a co-variate. Given that health plan cost-sharing policies in HSA-HDHPs and PDLs usually apply across enrollees regardless of age, and given that health plans, employers, policy makers, and families must make decisions about HSA-HDHPs and PDLs for both adults and children together, we felt it was important to evaluate the impact at the overall population level.

**Aim 3:** to examine the extent to which the response to HSA-HDHPs and PDLs is affected by the presence of other family members with asthma or other chronic conditions.

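### The plan does not commit to including plan group and outcomes when imputing income; imputing from the named variables alone would usually pull the Aim 2 income interaction toward zero

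*Combined protocol and SAP*

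**What the plan says.** In section C (Approach), under Methods to monitor and address missing data, member income is one of five variables listed as having missing values. PROC MI will impute it "using other available variables such as age, gender, census block level income, poverty, education etc", and the team will "conduct the statistical analyses under the assumption of missing at random". Imputation is one of three approaches: "a) multiple imputation, (b) modeling missingness as a member-level characteristic, and (c) excluding members with missing data". The reporting rule is "If findings differ, we will present results using all 3 methods in manuscripts or attached appendices". The team will also "explore certain Bayesian imputation techniques to handle missing data in case missing is not at random and compare the results". If credit-bureau data are missing too often, census-block poverty and education remain available. The figure of under 1% missing applies to those geocoded variables, and no rate is given for member income.

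Income has several roles:

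- Table 2 codes it as predictor, matching variable and stratifier.
- The Aim 2 hypothesis expects HSA-HDHPs without PDLs to worsen outcomes, "with widening of income and racial/ethnic disparities", and a PDL to lessen the disparities.
- The Aim 2 analysis uses three-way interactions (insurance type, study period, subgroup) "to test for statistical differences between subgroups in the impact of the change to an HSA-HDHP with PDL".
- Outcomes, item 5: "Financial burden due to OOP costs will be defined as annual family OOP costs as a percent of family income".

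**The concern.** An imputation model should contain the variables of the analysis that uses the imputed values. Here the analysis asks whether the switch effect differs by income. If income is drawn only from age, sex and census data, an imputed value carries no information about how that patient's outcome changed after the switch, beyond what those predictors convey. Among imputed patients the contrast between low-income and other patients is then mostly lost, and pooling them with observed patients dilutes the interaction.

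The risk is a real widening or narrowing of the income gap that is reported as smaller than it is, or missed. A programmer could follow the section as written and leave out the variables this test needs.

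Burden raises a related gap. It is a ratio with family income below the line, so it has no value when income is missing. Treating missingness as a covariate cannot supply one, and neither can census-block poverty or education.

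**Working it through.** The plan has no figure of its own to reproduce on this point: no missing-income rate, no interaction effect size, and no power for the income test in Table 3. The check is therefore conditional.

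**Closed form.** Let L be true low income (0/1), and let the switch effect be a + bL. A share m has income missing completely at random and imputed from predictors X alone.

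- Among observed patients, the difference in switch effect by income is b.
- Among imputed patients, the drawn value L* depends on L only through X. The difference by L* is b × Var(E[L|X]) / Var(L) = b × R2.
- Pooled: estimate / truth = (1 - m) + m × R2 = 1 - m(1 - R2).

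This assumes that neighbourhood does not separately modify the effect. R2 of 0.05 to 0.28 is an assumption.

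| Missing share m | R2 = 0.05 | R2 = 0.16 | R2 = 0.28 | Shrinkage |
|---|---|---|---|---|
| 5% | 0.9525 | 0.958 | 0.964 | 4-5% |
| 10% | 0.905 | 0.916 | 0.928 | 7-10% |
| 25% | 0.7625 | 0.790 | 0.820 | 18-24% |
| 40% | 0.620 | 0.664 | 0.712 | 29-38% |

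For example, 1 - 0.25 × (1 - 0.28) = 0.820.

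**Simulation inputs.**

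- From Table 3: group sizes of 18,000 vs 72,000 and 4,222 vs 16,888. Table 3 has no row for the contrast named in the interaction sentence (HSA-HDHP with PDL against a traditional plan), so the sizes are illustrative.
- Income gap in PDC change: -4.0 points, taken as the distance between the ends of the hypothesised 5-9% decrease. The documents give no interaction size.
- SD 0.42, not stated in the documents. It is consistent with the PDC rows of Table 3: 2.8016 × 0.42 × √(1/4,222 + 1/16,888) = 0.0202, against 2.0% stated; 2.8016 × 0.42 × √(1/18,000 + 1/72,000) = 0.0098, against 1.0% stated.
- Assumed: 30% low income, independent patients, five imputations combined by Rubin's rules. On change scores the three-way term reduces to plan group × low income.

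**Results, 18,000 vs 72,000, missing completely at random, true gap -4.0.**

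- Named variables only (census and age in the simulation): -3.7 to -3.9 at 5% missing, -3.6 to -3.75 at 10%, -3.1 to -3.35 at 25%, -2.45 to -2.85 at 40%. These agree with the formula; for example, 4.0 × 0.62 = 2.48.
- Plan group, outcome and their product added: -3.9 to -4.1 throughout.
- Complete cases: -3.9 to -4.1 throughout.

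**Other conditions.**

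- With missingness also dependent on plan group (about 29% missing), the named-variables model gave -2.5 against -4.0. The formula can therefore understate the loss when missingness differs by group.
- With no true gap (about 27% missing), the named-variables model was off by 0.04 points, with 0 rejections in 100.
- At 4,222 vs 16,888 with about 27% missing dependent on census, rejection rates were 75% with no missing data, 39% with named variables only, 59% with the fuller imputation and 58% with complete cases. Monte Carlo error is about 4 points.

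In every scenario run, missingness depended on nothing, on census variables or on plan group, and never on the outcome. No calculation was made for burden.

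**The case against.** The strongest reply is that the plan does not specify the narrow model. The list gives examples and stays open, and nothing excludes outcomes or plan group. A reader might infer that the plan leaves them out and that the Aim 2 income test is therefore biased. The documents do not support that reading; they support only that the plan makes no commitment. This part of the reply stands.

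Second, complete-case analysis is already planned and was unbiased in the scenarios run. A gap between it and the imputed result could expose the shrinkage. It also matched the fuller imputation on rejection rate (58% and 59%), so nothing here justifies demoting it. That stands too, but only while missingness does not depend on the outcome. The plan also does not say what counts as a difference between methods or which result decides the conclusion. The Bayesian work is exploratory and addresses data not missing at random, which is a separate problem.

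Third, the size rests on an unstated missing rate, and the worst cases might trigger the census-block fallback. This is fair, although no threshold is given. Fourth, movement toward zero is usual but not guaranteed: opposing effect modification by neighbourhood, or data not missing at random, could change it. This also stands.

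Finally, the imputation text concerns covariates, whereas burden is an outcome. That is correct, and it leaves the handling of burden with missing income unstated.

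**Conclusion.** The point holds in conditional form. The section names only demographic and census predictors and does not commit to the variables that the income interaction needs. If it is run on the named variables, the multiple-imputation estimate of that interaction usually shrinks by the amounts tabulated above: small at 5% missing, material from about 25%. The size rests on assumed values of m and R2, on missingness completely at random, and on no separate effect modification by neighbourhood.

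The harm is a real disparity understated or missed. The check does not indicate false disparities, nor that all three planned analyses share the problem. The case for change is that adding the analysis variables restored the true gap in the simulations, and that the plan does not say which of its three methods governs.

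**What to change.** In Methods to monitor and address missing data:

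1. State that the analysis-stage PROC MI model for income includes, besides the listed variables, plan group, baseline and follow-up outcomes (PDC, asthma ED and hospital events, OOP costs) and their products with plan group, or is run separately within intervention and control groups. No separate period term is needed, because income is imputed once per member and the baseline and follow-up outcomes carry the period information.
2. Use a separate imputation from baseline variables only for propensity matching, so that post-switch outcomes stay out of the match.
3. Keep complete-case analysis alongside, and say in advance which result governs the conclusion.
4. Report the share with missing income by group.
5. Do not use the missingness-indicator method for burden.

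The cost is SAP wording and the programming of two imputation models. No new data are needed.

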### **Analysis plan (IR-3; HT-2)**

**Aim 1:** to understand health care decision making and experiences of families with asthma under HSA-HDHPs and PDLs.

We will analyze qualitative data in iterative cycles of content analysis in the manner described by Patton. In the first, inductive phase of analysis, two coders will independently read initial transcripts multiple times in their entirety, and then analyze them through a process of open coding aimed at identifying broad topics of discussion. Through discussion with the larger study team, coders will identify codes of interest, and will structure subsequent interviews to explore these topics in greater depth. Over time, coders will refine codes and organize them into a codebook. When interviews begin to yield little new information (i.e., saturation), we will systematically apply codes to all transcripts using NVIVO.

In the second, deductive phase of analysis, we will consider data code-by-code to identify areas of convergence and divergence by insurance type (e.g., perceptions of medication affordability between participations with high-deductible versus traditional health plans). We will also consider data across codes by our three participant categories (i.e., patient, parent, patient and parent). We will describe emergent codes thematically, selecting representative quotations to illustrate key themes. We will then re-read transcripts to test identified themes to check for "dissenting views," or exceptions to overall themes, that might require additional analysis or discussion. To conduct "member checking," we will present our themes to AAFA partners, using facilitated discussion to elicit and incorporate their views in our analysis.

Findings will inform quantitative analyses for Aims 2-4. Outcomes of interest identified in the interviews will be added to Aim 2-4 where possible with claims data. Findings related to intrafamilial trade-offs will be used to refine analyses for Aim 3, and findings related to financial burden will be used to refine analyses for Aim 4.

**Aim 2:** to examine the impact of HSA-HDHPs with and without PDLs on use of asthma controller and rescue medications, and on adverse clinical outcomes (asthma-related emergency department (ED) visits and hospitalizations), overall and for vulnerable subgroups (low-income and racial/ethnic minority patients).

*Hypothesis (see Figure 2): Enrollees with asthma in HSA-HDHPs without PDLs will have worse adherence to controller medications, greater need for rescue medications, and higher rates of asthma-related ED visits and hospitalizations, with widening of income and racial/ethnic disparities; the addition of a PDL will improve use of controllers and rescue medications, reduce ED and hospitalization rates, and lessen disparities.*

Analyses will compare changes in outcomes from baseline to up to three years of follow-up among 1) asthma patients switched to HSA-HDHPs without PDLs from traditional plans vs. matched patients whose employers remain in traditional plans; and 2) patients switched to HSA-HDHPs with PDLs from traditional plans vs. matched controls remaining in HSA-HDHPs without PDLs. Sensitivity analyses will compare patients switched to HSA-HDHPs with PDLs from traditional plans vs. those who remain in traditional plans to examine the combined impact of both increasing the deductible and gaining a PDL. We will use separate regression models to compare year-to-year changes for each intervention group relative to its matched control group, rather than including all patients in a single model with multiple interaction terms. For secondary analyses of enrollees in the larger set of plan types that include PDLs, we will compare enrollees who are switched from plans with no PDL to plans with a PDL vs. those who remain in plans without a PDL. These analyses will match and adjust for different baseline plan types and deductible levels.

We will begin by performing descriptive analysis using the full dataset of all enrollees with asthma and their family members to examine predictors and trends over time concerning insurance coverage type, asthma care utilization, and costs for asthma care. Then among the targeted study groups, we will compare baseline characteristics between study groups using chi-square, t-tests, and Poisson or quantile regression. We will next display each outcome as a monthly time series of rates or counts, comparing trends over time in the groups of interest. We will use both ITS and DiD frameworks for analyses. Presuming our matching approach will generate similar baseline trends in the intervention and control groups, we will use ITS to display results and DiD to convey effect estimates in a more intuitive manner than ITS estimates. Controlling for potential confounders, we will use generalized linear models (GLMs) to model the independent effect of switching to each of the two types of HSA-HDHPs (with or without PDLs) on the likelihood of each outcome, assessed by interacting insurance type and study period variables in models. Data from the same patients in successive years are correlated, as are data from individuals from the same family. Extended GLMs - generalized estimating equations (GEE) and generalized linear mixed models (GLMM) - are appropriate methods to adjust for this correlation and to examine changes in outcomes between baseline and follow-up.

Asthma controller medications are intended to be taken regularly, so we will examine controller medication adherence using ITS. We will test the statistical significance of level or trend changes following insurance plan type switch using GLM models, adjusting for seasonality and first-order autocorrelation between sequential monthly measurements using the empirical sandwich estimator. Our analytic model will compare the odds ratio of having the primary therapy in the category available each day before and after the coverage switch. Our key independent variables will be: month, period (before or after the benefit switch), and month after the plan switch, adjusting for the same covariates as above. In addition to modeling changes in adherence to controller medications generally, we will address the variation across health plans in the types of controller medications included in PDLs by conducting sub-analyses to examine changes in adherence to the specific controller medications that are included in the PDL and those that are not included in the PDL (Aerospan, Arnuity ellipta, Asmanex HFA, Aerobid, Azmacort). For patients using medications that are not included in the PDL, we will examine the degree to which patients change to medications that are included on the PDL.

For analyses of rescue medication use, we will focus on albuterol and levalbuterol inhaler users. We will limit the time period of interest to 2009-2017, as albuterol inhalers, the primary asthma rescue medication, became available only as higher-priced branded CFC-free medications as of 2009 due to the FDA ban on generic CFC-containing inhalers. The standardized number of rescue inhalers dispensed will be modeled as count data in difference-in-differences models. ITS models will be used to model changes in level and trend of monthly rates of rescue inhalers dispensed, as in our previous study. Because use of controller medications can affect need for rescue medications, we will add controller medication adherence as a co-variate; sub-analyses will stratify by controller medication use in the baseline period. We will also model the ratio of controller medications to total asthma medications. For analyses of asthma-related ED visits and hospitalizations, outcomes can be binary, counts, or continuous. We will use logistic GEE models to estimate the effect of switching to each type of HSA-HDHP on binary outcomes such as any asthma-related hospitalization. We will use negative binomial regression to model the effect for count outcomes such as ED visits. We will select the conditional mean and variance functions based on the actual data, using a log link with a Gamma error distribution. To inform final model specification, we will employ specification tests including the Pregibon Link test for non-linearity and a modified Park test to select the conditional variance function.

In all statistical models, we will include key individual-level predictors from Table 2 to adjust for potential confounding. To determine the impact of HSA-HDHP with and without PDLs on vulnerable populations (RQ-4) and test for heterogeneity of treatment effects among vulnerable populations (HT-1-4), we will first perform stratified analyses, comparing outcomes between intervention and control subgroups defined by the binary measures of the risk factors of interest (low income, minority race/ethnicity, moderate-severe asthma, presence of other chronic conditions (including co-morbid diagnosis of COPD; we will also conduct analyses limited to ages 4-50 to remove the effect of COPD co-morbid diagnoses), high ACG morbidity). We hypothesize that these vulnerable subgroups will have worse adherence, more frequent adverse clinical outcomes, and higher OOP costs. We will use three-way interaction terms (insurance type \* study period \* subgroup) to test for statistical differences between subgroups in the impact of the change to an HSA-HDHP with PDL vs. remaining in a traditional plan. Heterogeneity of treatment effect analyses for these key variables will be reported along with overall findings from the combined population. Given that we will be conducting sub-group analyses to test for heterogeneity of treatment effect based on race/ethnicity and income using three-way interaction terms, we elected to separate the analyses of heterogeneity of treatment effect by age group into Aim 3 (described below), rather than add a fourth interaction term to the analyses in Aim 2. In Aim 2 analyses, we will include

both adults and children together, with age included as a co-variate. Given that health plan cost-sharing policies in HSA-HDHPs and PDLs usually apply across enrollees regardless of age, and given that health plans, employers, policy makers, and families must make decisions about HSA-HDHPs and PDLs for both adults and children together, we felt it was important to evaluate the impact at the overall population level.

**Aim 3:** to examine the extent to which the response to HSA-HDHPs and PDLs is affected by the presence of other family members with asthma or other chronic conditions.

***Hypothesis:** Adults with asthma will disproportionately experience negative effects of HSA-HDHPs on adherence and outcomes relative to children with asthma (HT-2), as will patients who have other family members with asthma or other chronic conditions; differences will be mitigated by the addition of a PDL.*

Aim 3 will focus on intra-familial trade-offs in response to cost-sharing changes in HSA-HDHPs and PDLs, and on adult-child differences in response to HSA-HDHPs and PDLs. Analyses will use the same population, outcomes, study group comparisons, and modeling strategies as Aims 1 and 2 except that we will perform stratified analyses, comparing outcomes between intervention and control groups stratified by adult/child status (RQ-4). To statistically test for heterogeneity of treatment effect for adults vs. children (HT-1-3), we will use three-way interaction terms (insurance type \* study period \* adult/child) to test for statistical differences between adults and children in the impact of the change to an HSA-HDHP with PDL vs. remaining in an HSA-HDHP without PDL, and the change to an HSA-HDHP without PDL vs. remaining in a traditional plan. Analyses will be done at the individual level, but will include family-level variables listed in Table 2 as predictors of interest. Separately for adults and children, we will test the extent to which having another family member with asthma, another chronic condition, or high baseline family ACG morbidity modifies the impact of HDHPs and PDLs on study outcomes for an individual asthma patient. The primary predictor of interest will be the interaction between the family-level variable, study period, and study group.

We will conduct secondary analyses on the subset of families in the study population that have both an adult and child with asthma insured in the same family plan, and will assess whether adults and children within the same family are differentially impacted by HDHPs and PDLs by comparing outcomes between intervention and control groups in separate strata for adults and children (HT- 1-2, IR-5).

**Aim 4:** to examine the impact of HSA-HDHPs with and without PDLs on out-of-pocket (OOP) costs for patients with asthma.

***Hypothesis:** Enrollees with asthma in HSA-HDHPs without PDLs will have higher OOP costs and increased financial burden as measured by the percent of income spent on OOP costs; the addition of a PDL will diminish these adverse outcomes.*

Analyses will be similar to those of Aim 2, but for OOP cost outcomes. Our primary analyses of changes in OOP costs will use a DiD analytic framework. We will follow the same approaches as used in analyzing ED visits and hospitalizations, employing two-part models/zero-inflated negative binomial models to account for zero costs. We will use GEE or GLMM models to examine changes in outcomes between baseline and follow-up to model the independent effect of switching to each of the two types of HSA-HDHPs (with or without PDLs) on the likelihood of having financial burden (OOP cost greater than 5% of income).

